### Step 3. Formulas for T-score Transformation of Component Scores (Standard Form)

The third step involves transforming each component score to the norm-based (50, 10) scoring. This is accomplished by multiplying each aggregate component scale score by 10 and adding the resulting product to 50.

$$\begin{aligned} \text{Transformed Physical (PCS)} &= 50 + (\text{AGG\_PHYS} \times 10) \\ \text{Transformed Mental (MCS)} &= 50 + (\text{AGG\_MENT} \times 10) \\ \text{Transformed Role/Social (RCS)} &= 50 + (\text{AGG\_ROLE} \times 10) \end{aligned}$$

### Missing Data in an Individual Questionnaire

In the event that data is missing for an individual item from the scales of the SF-36v2® Health Status Survey, the average value of the completed items in the corresponding scale will be used as an estimate of the missing item. If more than 50 percent of the items from a scale are missing for an individual questionnaire, the corresponding deficient scale(s) will be excluded from analyses.

Items in each scale are given below:

SF-36v2 Scale	No. Items	Items	Minimum No. Non-Missing Items for Imputation of Missing Values
PF	10	3a, 3b, 3c, 3d, 3e, 3f, 3g, 3h, 3i, 3j	5
RP	4	4a, 4b, 4c, 4d	2
BP	2	7, 8	1
GH	5	1, 11a, 11b, 11c, 11d	3
VT	4	9a, 9e, 9g, 9i	2
SF	2	6, 10	1
RE	3	5a, 5b, 5c	2
MH	5	9b, 9c, 9d, 9f, 9h	3

#### Example Showing the Mechanics of Imputation Technique:

Suppose for a subject the items 1, 3b, 3e, 3f, 4a, 4b, 11b, 11d, 5a and 5b are missing. First group the missing items according to the scale:

- GH: Items 1, 11b, 11d
- PF: Items 3b, 3e, 3f
- RP: Items 4a and 4b
- RE: Items 5a and 5b

GH consists of 5 items and 3 are missing. That is only 2 have non-missing scores. Since at least half of the items are not non-missing, missing items 1, 11a and 11d cannot be imputed. Therefore for this subject, the General Health scale score will be missing.

PF consists of 10 items. So, for this subject 7 of the items are non-missing. That is, at least half of the items are non-missing. Therefore replace the missing Items 3b, 3e and 3f scores

by the average score of the non-missing items, i.e., replace by  $(3a + 3c + 3d + 3g + 3h + 3i + 3j) / 7$ .

RP consists of 4 items and two are missing. So at least half are non-missing. Therefore replace the missing item scores 4a and 4b by  $(4c+4d) / 2$ .

RE consists of 3 and two are missing. That is, more than half of the item scores are missing. Therefore, missing scores 5a and 5b cannot be imputed for this subject and thus RE scale score for this subject will be missing.

## 10.7 Appendix 7: Computation of WPAI Scale Score

### Work Productivity and Activity Impairment Questionnaire: WPAI

In this study, the following scoring method are applied. These scoring method are based on the specific health problem version of WPAI (WPAI:SHP).

Question Number	Contents
1.	1.Are you currently employed (working for pay)?
2.	2.During the past seven days, how many hours did you miss from work because of problems associated with your rheumatoid arthritis?
3.	3.During the past seven days, how many hours did you miss from work because of any other reason, such as vacation, holidays, time off to participate in this study?
4.	4.During the past seven days, how many hours did you actually work?
5.	5.During the past seven days, how much did your rheumatoid arthritis affect your productivity while you were working?
6.	6.During the past seven days, how much did your rheumatoid arthritis affect your ability to do your regular daily activities, other than work at a job?

Scores:

Multiply scores by 100 to express in percentages.

- Percent work time missed due to problem:  $Q2/(Q2+Q4)$
- Percent impairment while working due to problem:  $Q5/10$
- Percent overall work impairment due to problem:  
 $Q2/(Q2+Q4)+[(1-(Q2/(Q2+Q4)))\times(Q5/10)]$
- Percent activity impairment due to problem:  $Q6/10$

## 10.8 Appendix 8: AE of Special Interest

1. Serious Infections
  - AE which belongs to SOC of Infections and infestations (10021881) and regarded as serious.
2. Malignancies

Following PT terms are included.

Diffuse large B-cell lymphoma (10012818), Bladder cancer (10005003), Breast cancer (10006187), Carcinoma in situ (10061450), Colon cancer (10009944), Gastric cancer (10017758), Renal cancer (10038389), Squamous cell carcinoma (10041823), Small cell lung cancer stage unspecified (10041071), Extraskelatal chondrosarcoma (10015838), Lymphoma (10025310), Thyroid cancer (10066474).
3. Herpes Zoster Related Disease (Herpes Zoster and Varicella)

Following PT terms are included.

Herpes zoster (10019974), Herpes zoster iridocyclitis (10019980), Herpes zoster ophthalmic (10019983), Herpes zoster multi-dermatomal (10058428), Herpes zoster infection neurological (10061208), Herpes zoster oticus (10063491), Herpes zoster disseminated (10065038), Encephalitis post varicella (10014603), Varicella (10046980), Varicella post vaccine (10063522).
4. Herpes Zoster

Following PT terms are included.

Herpes zoster (10019974), Herpes zoster iridocyclitis (10019980), Herpes zoster ophthalmic (10019983), Herpes zoster multi-dermatomal (10058428), Herpes zoster infection neurological (10061208), Herpes zoster oticus (10063491), Herpes zoster disseminated (10065038)
5. Varicella

Following PT terms are included.

Encephalitis post varicella (10014603), Varicella (10046980), Varicella post vaccine (10063522).
6. Infections That Require Intravenous Anti-infectious Therapy

All PTs which belong to SOC of Infections and Infestations (10021881) for which there is an intravenous concomitant medication (antibiotics, antivirals, antifungals, etc.) associated with that event for that patient.

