Because ASP015K is an immunosuppressive agent, it may increase the risk of infections and reactivation of latent, chronic infections. In particular, excessive immunosuppression can lead to serious infections. Of note is the fact that Xeljanz[®] (tofacitinib) 5 mg, a member of the class of JAK inhibitors to which ASP015K belongs, have been associated with new onset or aggravation of serious infections such as tuberculosis, pneumonitis, sepsis, viral infections, and opportunistic infectious diseases including fungal infections. In addition, several cases of malignant tumors have been reported, although their causal relation to the agent has not been established. Based on the data pooled from 5 domestic and overseas comparative studies of Xeljanz[®] (tofacitinib) 5 mg, the incidence density of malignancies (excluding non-melanoma skin cancers) among RA patients treated with 5 mg BID for a maximum of 1 year was 0.55/100 person-years (incidence rate 0.5% < 5/1216) [Xeljanz[®] Pharmaceutical Interview Form (in Japanese)].

These findings suggest that investigators pay particular attention to the possible development of infections and malignancies and take appropriate measures. Three cases of malignancies (stomach cancer, uterine sarcoma, chronic myelogenous leukemia) have been reported as of the cut-off date of 5 December 2013, from completed and ongoing national and international studies of ASP015K. Only the case of uterine sarcoma was judged as related to ASP015K.

In the Japanese clinical trial in patients with moderate to severe RA (015K-CL-RAJ1), 50 mg and higher doses of ASP015K significantly improved the ACR20 response rate versus placebo. Xeljanz[®] (tofacitinib) 5 mg, which acts via the same mechanism as ASP015K, was approved by the US FDA in 2012 for the treatment of adult patients with moderate to severe RA who had an inadequate response to or are intolerant of MTX. In March 2013, Xeljanz[®] (tofacitinib) 5 mg tablets was authorized for marketing in Japan for treating RA patients who had an inadequate response to conventional therapies. Therefore, a potential benefit of JAK inhibitor ASP015K is to improve RA.

One can also expect that long-term use of ASP015K will improve QOL of RA patients by successfully controlling the RA disease activity over an extended period.

- CONFIDENTIAL -

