APPENDIX <3>: EVENTS ALWAYS CONSIDERED SERIOUS

If any of the following events occurs during the study, it should be regarded as an SAE and must be reported in accordance with Section [5.5.5](#) Reporting of Serious Adverse Events (SAEs).

- Acute hepatic failure
- Renal failure acute
- Acute respiratory failure
- Agranulocytosis
- Anaphylactic reaction, anaphylactic shock
- Malignant tumor
- Aplastic anaemia
- Endotoxic shock (confirmed or suspected)
- Confirmed or suspected transmission of infectious agents by marketed product
- Congenital anomalies
- Hepatic necrosis
- Malignant hypertension
- Pulmonary fibrosis
- Pulmonary hypertension
- Sclerosing syndromes
- Convulsion (only central neurological seizure)
- Torsades de pointes
- Toxic epidermal necrolysis
- Ventricular fibrillation

Note: Hy's Law cases should be regarded as SAE.

See Appendix 4 "Liver Safety Monitoring and Assessment."

- CONFIDENTIAL -

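### The Malignancies event of special interest is a closed list of 12 preferred terms with no uterine and no leukaemia term, although both tumour types have already been reported with this drug

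*SAP*

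**What the plan says.** The Malignancies item in SAP 10.8 (Appendix 8) opens with "Following PT terms are included" and then gives the terms. The first stretch of the list reads "Diffuse large B-cell lymphoma (10012818), Bladder cancer (10005003), Breast cancer (10006187), Carcinoma in situ (10061450), Colon cancer (10009944". After that the list goes on with "Gastric cancer (10017758), Renal cancer (10038389), Squamous cell carcinoma (10041823), Small cell lung cancer stage unspecified (10041071". It closes with these entries: "Extraskelatal chondrosarcoma (10015838), Lymphoma (10025310), Thyroid cancer (10066474". The item contains nothing else. In the same appendix, serious infections and infections needing intravenous treatment are defined through the whole infections system organ class.

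Two sets of results rest on this item. SAP 7.5.1.1 and Table 17 in SAP Appendix 3 use it for the number and percentage of subjects with the event. SAP 7.5.1.2 uses it for the Definition 1 rate per 100 patient-years with a 95% confidence interval. In the SAP Appendix 3 tables, placebo is included for Week 0 to Week 12, and the overall period shows the 100 mg and 150 mg groups only.

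Protocol 1.4 states: "Three cases of malignancies (stomach cancer, uterine sarcoma, chronic myelogenous leukemia) have been reported as of the cut-off date of 5 December 2013". It adds: "Only the case of uterine sarcoma was judged as related to ASP015K". Protocol Appendix 3 includes malignant tumor, without any list of types, among the events covered by the rule "If any of the following events occurs during the study, it should be regarded as an SAE".

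**The concern.** Malignancy is one of the risks that Protocol 1.4 asks investigators to watch for, and the SAP gives it a count and a rate of its own. A reader of the report will take that line as the trial's malignancy result. A narrow disease can reasonably be defined by naming its terms. Malignancy is broad, and this list omits two tumour types that the sponsor's own protocol reports with this drug, one of them judged related to it. It also has no catch-all, so an ovarian, prostate, pancreatic or non-small-cell lung cancer would not count either. The protocol's concept is any malignant tumor; the SAP's is 12 codes. Events of this kind are likely to be few, so one event in or out can change the reported rate substantially.

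**Working it through.** The plan states no figure on this point, so the check is a count and a match, followed by an illustration of sensitivity.

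**1. Count the terms.** The three runs quoted above hold 5, 4 and 3 terms: 5 + 4 + 3 = 12.

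**2. Match the tumours in Protocol 1.4 to the list.**

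| Tumour in Protocol 1.4 | Judged related | Term in SAP Appendix 8 |
|---|---|---|
| Stomach cancer | No | Gastric cancer |
| Uterine sarcoma | Yes | None (the only sarcoma term is a chondrosarcoma) |
| Chronic myelogenous leukemia | No | None |

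One of three matches. Searching the 12 terms for the fragments uter, leuk and myelo finds nothing.

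**3. Trace where an unlisted malignancy would go.**

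| Output | Included? |
|---|---|
| Subject listings of all adverse events (SAP 7.5.1) | Yes |
| Treatment-emergent events by class and term (SAP 7.5.1.1) | Yes |
| Serious treatment-emergent events (SAP 7.5.1.1, with Protocol Appendix 3) | Yes |
| Definition 2 rate by class and term (SAP 7.5.1.2) | Yes, where analyzable |
| Malignancies count (SAP 7.5.1.1, Table 17) | No |
| Definition 1 rate with 95% interval (SAP 7.5.1.2) | No |

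Definition 2 is only a partial substitute. It counts events rather than subjects, it is not restricted to malignant events, and the interval in SAP 7.5.1.2 is specified for the events of special interest only.

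**4. Illustrate how much one event weighs.** Assume 340 patient-years on active drug: 170 subjects × 2 groups × 1 year, with no dropout. The SAP interval is 100 × exp(log(A/T) ± 1.96 × √(1/A)), with A the number of subjects with an event and T taken here in patient-years.

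- A = 3: rate 3/340 × 100 = 0.88, interval 0.28 to 2.74.
- A = 1: rate 1/340 × 100 = 0.29, interval 0.04 to 2.09.
- A = 0: log(0/T) and 1/A are undefined, so the formula gives no interval.

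With 10% dropout the assumed total is 306 patient-years, and the rates rise by 340/306 − 1 = 11%. For scale, Protocol 1.4 quotes 0.55 malignancies per 100 person-years for tofacitinib, excluding non-melanoma skin cancer. If that rate applied here, the expected number would be 0.55 × 340/100 = 1.9 events (1.7 at 306). These figures show only that each event matters. They do not forecast how many would be unlisted.

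**The case against.** The strongest reply is that no case is hidden. Step 3 shows four outputs that would still carry an unlisted cancer. In addition, malignant tumor is a discontinuation criterion in Protocol 3.4, so such a case should also reach the table of events leading to permanent discontinuation, and the DSMB reviews unblinded safety data. All of this stands. It limits the loss to one subtotal and its rate, neither of which is formally tested.

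The second reply concerns timing. The SAP was finalised on 18 January 2018, in the last month of the planned study period and before unblinding. Terms as specific as small cell lung cancer of unspecified stage look more like coded events already seen than a list drawn up in advance. If so, the list may already cover every coded case. That is plausible, but it is inference: the SAP gives no origin for the list and no rule for a term coded or recoded afterwards.

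Three stronger readings are tempting, and the documents do not support them.

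- A reader might infer that two thirds of malignancies will be missed. The three cases come from other studies with a cut-off in December 2013, before this trial's planned start in July 2014. They show a gap in the list and do not estimate a proportion for this trial.
- A reader might infer that the list can only undercount. It includes carcinoma in situ and an unqualified squamous cell carcinoma, so against a definition limited to invasive cancer, or one excluding non-melanoma skin cancer, it could also add events.
- A reader might infer a bias in favour of the drug over placebo. In the SAP Appendix 3 tables the only placebo comparison of this event is Week 0 to Week 12, where the same list applies to every group. What an omission can lower is an absolute rate in a dose group.

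**Conclusion.** The point holds as a defect in the definition. As written, the rule leaves out of the Malignancies count and its Definition 1 rate any cancer coded outside the 12 terms, including the tumour type already judged related to the drug. For each such case the effect is downward, and in the overall period it falls on an absolute rate for the dose groups. The size of any undercount in this trial cannot be derived from the documents, and zero is possible. The conclusion rests on the text of Appendix 8 being the operative definition and on no catch-all existing elsewhere in the SAP; none was found. The primary and other efficacy analyses are not affected.

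**What to change.** Amend SAP Appendix 8 before unblinding, as follows:

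- Define Malignancies as all treatment-emergent events in the neoplasm system organ class that are judged malignant in a blinded review of coded terms. The Case Review Meeting already takes advice from a medical expert (Protocol 7.2 and 7.9) and can do this.
- Reconcile the result with the serious adverse events reported as malignant tumor under Protocol Appendix 3.
- State whether carcinoma in situ and non-melanoma skin cancer count, so that the rate can be set beside figures such as the one in Protocol 1.4.
- Keep the 12 terms as examples only, and say where they came from.

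The cost is a wording change and a short blinded term review, with no new data collection. If the list already covers every coded malignancy, no malignancy is added; the count could then change only through the stated handling of carcinoma in situ and non-melanoma skin cancer.

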3.4 Discontinuation Criteria for Individual Subjects

A discontinuation is a subject who enrolled in the study and for whom study treatment is permanently prematurely discontinued for any reason.

The subject is free to withdraw from the study treatment and/or study for any reason and at any time without giving reason for doing so and without penalty or prejudice. The investigator is also free to terminate a subject's involvement in the study at any time if the subject's clinical condition warrants it.

The Appendix 4 entitled "Liver Safety Monitoring and Assessment" describes liver function tests raised that provide grounds for discontinuation. Refer to Appendix 4 concerning the measures to take for increases in liver function test parameters.

The investigator/sub-investigator should discontinue the study if any of the following occurs:

1. The subject withdraws consent.
2. The investigator/sub-investigator judges that the study drug is not sufficiently effective and the treatment method needs to be changed.
3. Symptomatic CPK elevation ($> 1.5 \times \text{ULN}$ accompanied with severe and unusual episodes of myalgia, muscular weakness, or muscle twitching).
4. Any case of myopathy involving severe and unusual episodes of myalgia, muscular weakness, or muscle twitching that persists for no less than, or aggravates rapidly within, 2 weeks, regardless of the CPK level.
5. A previously HBV-infected patient with positive HBe antibody, positive HBs antibody, or both has been shown positive for HBV-DNA during the study.
Attention should be paid that abrupt discontinuation of immunotherapy may cause fulminant or severe liver failure. Therefore, if the subject manifests HBV reactivation, the investigator/sub-investigator will administer nucleoside analogs without delay according to the "Proposal for Management of Rheumatic Disease Patients with Hepatitis B Virus Infection Receiving Immunosuppressive Therapy" (Japan College of Rheumatology). The investigator/sub-investigator will carefully decide whether to continue or discontinue the study drug and concomitant DMARDs in consultation with the hepatology specialist.
6. Malignant tumor
7. The subject develops a serious infection or other AEs, and continued administration of the study drug is not deemed appropriate in the subject's best interest by the investigator/sub-investigator.

- CONFIDENTIAL -

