## 6.2 Safety Variables

- AEs
- Vital signs (body temperature, pulse rate and blood pressure in sitting position)
- Body weight
- Central ECG
- 12-lead ECG
- Central electrocardiogram
- Chest radiography
- Laboratory assessments

**Treatment emergent adverse events** (TEAEs) will be defined as any adverse event that started or worsened in severity after initial dose of study drug through Week52 or Withdrawal.

AE for the subjects who switched ASP015K 100 mg or ASP150 mg from Placebo at Week 12 or Week 28 will be handled as follows.

- AE onset before the first dose of week12 study drug will be considered to be occurred at Placebo.
- AE onset after the first dose of week12 study drug before the first dose of week28 study drug will be considered to be occurred at Placebo if the subject did not switch Placebo at Week 12. Else, if the subject switched ASP015K 100 mg or 150 mg at Week12, then the AE onset after the first dose of week12 study drug before the first dose of week28 study drug will be considered to be occurred at ASP015K 100 mg or 150 mg.
- AE onset after the first dose of week28 study drug will be considered to be occurred at ASP015K 100 mg or 150 mg, which is switched treatment from Placebo.

A drug-related TEAE is defined as any TEAE with possible, probable or missing relationship to study drug as assessed by the investigator. Moreover, any TEAE with missing relationship to study drug or reference drug was counted as drug related (probable).

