#### **7.2.3 Previous and Concomitant Medications**

Previous DMARD medications will be summarized as described in 7.2.2.3.

In addition to this, previous and concomitant medications will be coded using WHODDE(B2) (V2011SEP) and summarized by "Non-Biologic DMARD" and "previous and concomitant medications except for Non-Biologic DMARD" with preferred WHO name, respectively from following CRF page. Concomitant medications are defined as any drug medications after the first dose of study drug up to the last dose date of study drug and before the last efficacy evaluation at Week52 or Withdrawal.

[Concomitant Medication 2B -page of the CRF]

[Concomitant Medication (Non-Biologic DMARD)]

Subjects taking the same medication multiple times will be counted once per medication.

All summaries will be provided for SAF.

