### 7.5.1 Adverse Events

If an AE occurs on the same date as the initial dose date, the subject will be asked to select one of the following (see the eCRF page for AE): onset before initial dose of study drug,

onset after initial dose of study drug. Any AEs occurring after initial dose of study drug through the follow-up period will be considered treatment emergent.

Adverse events will be coded using the Medical Dictionary for Regulatory Activities (MedDRA).

All adverse events reported during the study period will be presented in subject listings.

Only TEAEs in the study period will be analyzed, and 2 types of analyses will be performed: TEAE occurrence analysis and TEAE per 100 patient-years analysis, as described below. TEAE occurrence analysis will be displayed by whole treatment period and by the following period. Primarily, TEAE occurrence analysis for Week 0 to Week 12 will be conducted in the view of comparison with placebo.

TEAE occurrence analysis for overall treatment period will be conducted in focus for ASP015K dose groups.

1. Week 0 to Week 12
2. Week 12 to Week 28
3. Week 28 to Week 52 or Later

TEAE per 100 patient-years analysis will be displayed above category, and by Week 0 to Week 12, and overall period.

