#### Definition 1:

TEAEs per 100 PYs =  $100 \times (\text{Number of subjects who had at least 1 incidence} / \text{Total PYs})$

Total PYs will be calculated by summing individual subjects' durations.

If subjects had at least 1 predefined AE, then the duration of these subjects are summed as from initial dose up to first incidence of predefined AEs.

If subjects had no predefined AE, then the duration of these subjects are summed as from initial dose through follow-up. Summed duration will be divided by 365.25 to represent per year.

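### Read literally, the SAP's event for infections needing intravenous therapy omits an on-treatment infection that ends dosing if the IV drug starts after the last-dose date

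*SAP*

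**What the plan says.** SAP 10.8 (Appendix 8), item 6, defines infections that require intravenous anti-infective therapy. An event in the infections system organ class qualifies only if "there is an intravenous concomitant medication (antibiotics, antivirals, antifungals, etc.) associated with that event for that patient".

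The SAP defines concomitant medication once, in 7.2.3: "Concomitant medications are defined as any drug medications after the first dose of study drug up to the last dose date of study drug". The same sentence then sets a second limit on the timing: "and before the last efficacy evaluation at Week52 or Withdrawal". The two limits are joined by 'and', so the second narrows the window.

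The adverse event (AE) sections use other windows:

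- SAP 7.5.1: "Any AEs occurring after initial dose of study drug through the follow-up period will be considered treatment emergent".
- SAP 6.2: a treatment-emergent event is one that "started or worsened in severity after initial dose of study drug through Week52 or Withdrawal".
- SAP 7.5.1.2, Definition 1 (the patient-year rate used for this event): "If subjects had no predefined AE, then the duration of these subjects are summed as from initial dose through follow-up".

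Appendix 3 of the SAP lists item 6 for subject counts (Table 17) and for the patient-year analysis. Weeks 0 to 12 are shown for placebo, 100 mg and 150 mg, and the overall period for 100 mg and 150 mg only.

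**The concern.** The event window and the medication window do not match. An infection can be treatment emergent and treated intravenously, and still fail item 6 because the IV drug began after the final dose of study drug. The case is foreseeable: criterion 7 in Protocol 3.4 lists as a ground for discontinuation "The subject develops a serious infection or other AEs, and continued administration of the study drug is not deemed appropriate". If dosing is only suspended and later resumed, the same IV course falls before the eventual last dose and qualifies. Whether an infection counts can therefore depend on whether the patient went back on study drug, which is not what the event is meant to measure.

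At stake is the accuracy of one reported adverse event of special interest, and of its rate per 100 patient-years with 95% confidence interval, for a drug that Protocol 1.4 describes as immunosuppressive.

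**Working it through.** The documents state no expected count or rate for item 6, so there is no figure to reproduce. The check applies the stated windows to cases and then shows scale with assumed counts.

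**Rule applied.** IV therapy qualifies if it starts after the first dose, on or before the last-dose date, and before the last efficacy evaluation (SAP 7.2.3).

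| Case | Treatment emergent? | Qualifying medication? | Counted in item 6? |
|---|---|---|---|
| Onset and last dose Day 100, permanent stop, IV from Day 101, last efficacy evaluation Day 102 | Yes, under 6.2 and 7.5.1 | No | No |
| Same, but IV from Day 100 | Yes | Yes | Yes |
| Onset Day 100, drug suspended, IV from Day 101, dosing resumed to Day 364 | Yes | Yes | Yes |
| Last dose Day 364, onset Day 380 in follow-up, IV from Day 381 | Yes under 7.5.1, no under 6.2 | No | No |

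The second row holds only if the IV start also precedes the last efficacy evaluation.

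**How easily the first case arises.** Under Protocol 5.1.6 subjects attend scheduled visits without having taken that day's dose, and under Protocol 5.1.1 they take it after the assessments. Suppose an infection with onset on Day 112 is found at the Week 16 visit (Day 113) and the drug is stopped for good. The last dose was then normally on Day 112. IV therapy begun on Day 113 is already outside the window, with no overnight delay.

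**Person-time.** Had that infection been counted, the subject would contribute 112 days, up to first incidence. When it is missed, the subject is treated as event-free through follow-up. With early termination on Day 113 and follow-up 28 days later, that is 113 + 28 = 141 days. The excess is 141 − 112 = 29 days, or 29/365.25 = 0.08 patient-years. The lost event therefore matters far more than the added person-time.

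**Scale, on assumed figures.** Take 170 subjects × 0.9 years = 153 patient-years and 10 true events. The rate is 100 × A/153, and the SAP 7.5.1.2 interval is rate × exp(±1.96 × √(1/A)).

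| Fraction missed | A | Rate per 100 patient-years | 95% CI |
|---|---|---|---|
| 0 | 10 | 6.54 | 3.52 to 12.15 |
| 10% | 9 | 5.88 | 3.06 to 11.31 |
| 30% | 7 | 4.58 | 2.18 to 9.60 |
| 50% | 5 | 3.27 | 1.36 to 7.85 |

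Person-time is held fixed. Even with five events missed, the added 5 × 0.08 = 0.4 patient-years is about 0.3% of 153. The rate falls by essentially the fraction missed.

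**The case against.** The strongest objection is that the 7.2.3 window was written for the coded medication summaries. It is not in the SAP's list of key terms, and Appendix 8 does not cite it. Item 6 asks for a link to the event and states no dates. Protocol 5.1.2 starts the concomitant medication survey at first dose and gives no end, and Protocol 5.5.1 has the treatment of each AE recorded. A programmer could reasonably link any IV record to the infection and lose nothing. This stands as a limit: the exclusion follows from the literal text and is not certain to occur. It does not remove the point, because 7.2.3 is the only definition the SAP gives, and two programmers could obtain different counts from the same text. The two-day allowance after the last dose in SAP 7.11.5 does not settle it, since it governs the schedule of safety assessments and does not redefine medication.

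The second objection is that such infections remain visible elsewhere. That is correct. Item 1 of Appendix 8 takes any infection regarded as serious, with no medication condition, and Protocol 5.5.2 makes hospitalisation for an AE serious. Item 1 has its own counts and patient-year rate. Events leading to permanent discontinuation are also tabulated by system organ class and preferred term.

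A reader might go further and infer any of the following, none of which the documents support:

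- *Serious infections disappear from the safety analysis.* They do not, for the reasons just given.
- *Every infection that ends treatment is dropped.* Only those whose IV therapy starts outside the 7.2.3 window are.
- *The comparison with placebo is biased in favour of the drug.* That needs the loss to differ between arms, and nothing in the documents shows it. Appendix 3 also limits the placebo comparison of this event to Weeks 0 to 12.
- *Follow-up infections are wrongly lost.* That holds only if 7.5.1 sets the treatment-emergent window. Under 6.2 they lie outside the treatment-emergent analyses anyway.

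**Conclusion.** The point holds in a limited form. On the SAP's literal definitions, an infection that begins on treatment and leads to permanent discontinuation is omitted from item 6 when IV therapy starts after the last-dose date, and the subject is carried in the Definition 1 denominator as event-free. This core case does not depend on the conflict between 6.2 and 7.5.1, because onset on treatment is treatment emergent under both.

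The undercount is confined to item 6 and its patient-year rate. Its size and any difference between arms cannot be derived from the documents. The tabulated 10%, 30% and 50% losses, the 10 events and the 153 patient-years are all assumptions, used only to show that the rate falls roughly in proportion to the events missed. The conclusion also assumes that the 7.2.3 definition is carried into Appendix 8, which the SAP neither states nor rules out. No primary endpoint is affected.

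**What to change.** In Appendix 8 item 6, replace the reference to an intravenous concomitant medication with: *any intravenous anti-infective recorded as given for that event, started on or after its onset and up to the end of AE collection, irrespective of the last dose date of study drug*. Add to 7.2.3 that its window applies to the medication summaries only.

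Separately, reconcile SAP 6.2 and 7.5.1 on whether the treatment-emergent period ends at Week 52 or withdrawal, or runs through follow-up. That decides whether infections arising in follow-up can enter item 6 at all.

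The cost is one sentence in each place and one programming condition. The data should already exist: Protocol 5.4.3 collects AEs to the end of follow-up or the start of extension dosing, Protocol 5.5.1 records how each was treated, and Protocol 5.1.2 sets no end to the medication survey. The reported item 6 rate may be slightly higher. The medication tables do not change.
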